18.0 ADVERSE EVENT REPORTING AND PROCEDURES

18.1 Definition of Adverse Events and Serious Adverse Events

An **adverse event** (AE) is any untoward medical occurrence in humans, whether or not considered study medication related which occurs during the conduct of the clinical trial. Any change from baseline in clinical status, ECGs, lab results, x-rays, physical examination, etc., that is considered clinically significant by the PI are considered AEs.

Suspected adverse reaction is any adverse event for which there is a reasonable possibility that the study medication caused the adverse event. A reasonable possibility implies that there is evidence that the study medication caused the event.

Adverse reaction is any adverse event caused by the study medication.

An **adverse event, suspected adverse reaction, or adverse reaction** is considered "**serious**" if, in the view of the PI it:

- 1) Results in a death
- 2) Is life-threatening
- 3) Requires inpatient hospitalization or prolongation of existing hospitalization
- 4) Results in persistent or significant incapacity or substantial disruption of the ability to conduct normal life functions
- 5) Is an important medical event that may not result in one of the above outcomes, but may jeopardize the health of the study participant or require medical or surgical intervention to prevent one of the outcomes listed in the above definition of serious event.

18.2 Definition of Expectedness

Any adverse event is considered “unexpected” if it is not listed in the package insert or is not listed at the specificity or severity that has been observed.

18.3 Medical and Psychiatric History

A thorough review of the participant's medical and psychiatric history of any chronic, acute, or intermittent preexisting or current illness, diseases, symptoms, or laboratory signs should be undertaken to avoid reporting pre-existing conditions as new AEs and to assist in the assessment of worsening in intensity or severity of these conditions that would indicate an AE. Stable chronic conditions which are present prior to clinical trial entry and do not worsen are not considered AEs.

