10. STUDY ASSESSMENTS

10.1 Overview:

The baseline and follow-up assessments for this study attempt to balance the benefits of comprehensive data collection against the feasibility of collecting data in often chaotic and pressured environment of the Emergency Department.⁷³ A cumbersome assessment process is also likely to impede the successful completion of the study through an adverse effect on recruitment nor would it model real-world clinical practice. If this intervention is to be successful it must not only be shown to be effective but also feasible and pragmatic. Excluding collection of a study patient participant characteristics and locator information, the patient's baseline data will include a brief assessment of HIV risk and attitudes toward PrEP. The total expected time burden for the screening assessments is 30-60 minutes. Assessments collected at 30, 60, and 90 days post study enrollment will be similar.

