10.5.7 STAR*D PRISE

The STAR*D PRISE measure is a validated instrument designed to measure side-effects of common antidepressant medications but has been used widely as a general measure of medication side-effects. This will be administered at each follow-up assessment for those patients taking PrEP.

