2. Medications at the time of event: Yes No Unknown

Be sure to assess for dosage and date of last dose for the study medication, and any prior/concomitant medications as needed.

Medication (Generic Name)	Indication

3. Treatments for the event: Yes No Unknown

Treatment	Indication	Date Treated (mm/dd/yyyy)

4. Labs/tests performed in conjunction with this event: Yes No Unknown

Lab/Test	Findings	Date of Test (mm/dd/yyyy)

5. Follow-up:

Include labs/test results as they became available, clinical changes, consultant diagnosis, etc.

Comments:

Study staff completing form:

Date completed:

Patient ID

Date

 / /
MM DD YYYY

Level

Week in
level

Please indicate all symptoms you have experienced in the past week. These symptoms may or may not have been caused by your treatment.

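### No pre-PrEP symptom status matched to PRISE is scheduled, so persistent background symptoms risk misattribution to PrEP and worsening has no earlier rating to be judged against

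*Combined protocol and SAP*

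**What the plan says.** Section 18.1 defines an adverse event in two clauses. An AE "is any untoward medical occurrence in humans, whether or not considered study medication related" that arises while the trial is running. It also includes "Any change from baseline in clinical status, ECGs, lab results, x-rays, physical examination, etc., that is considered clinically significant by the PI".

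Section 18.3 asks staff to keep old conditions apart from new ones. A review of each participant's "medical and psychiatric history of any chronic, acute, or intermittent preexisting or current illness, diseases, symptoms, or laboratory signs should be undertaken". The same sentence gives the purpose: the review "should be undertaken to avoid reporting pre-existing conditions as new AEs and to assist in the assessment of worsening in intensity or severity". Section 18.3 adds that "Stable chronic conditions which are present prior to clinical trial entry and do not worsen are not considered AEs". It names no form, visit or time for that review.

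On baseline data, 10.1 states that, apart from participant characteristics and locator information, "the patient's baseline data will include a brief assessment of HIV risk and attitudes toward PrEP". Section 9.3 lists four enrollment measures: locator form with demographics, satisfaction, PrEP attitudes and sexual behavior. Section 10.4 describes the same content.

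PRISE appears among the follow-up assessments in 9.5, which fall at days 30, 60 and 90. Section 10.5.7 says of it: "This will be administered at each follow-up assessment for those patients taking PrEP". The printed form, placed after Appendix 10, asks for all symptoms in the past week and tells the participant: "These symptoms may or may not have been caused by your treatment".

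**The concern.** Sections 18.1 and 18.3 ask for two judgements: whether a symptom was there before the trial, and whether it has become worse. Both need a starting value. For the symptoms on PRISE, the plan schedules none.

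The population makes this more than a formality. Section 16.0 gives priority to patients whose complaint suggests PrEP eligibility, with genital discharge, overdose and drug withdrawal as examples. PRISE includes painful and frequent urination, nausea/vomiting, diarrhea, tremors and increased perspiration. Some participants may well have such symptoms for reasons unrelated to PrEP. Nausea, vomiting and diarrhea are also the side effects that 12.2 names for the study drugs, so background and drug effect can look alike.

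At stake is whether the side-effect data can be interpreted. A pre-PrEP rating cannot be collected once PrEP has started.

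**Working it through.** The plan states no figure on this point, so there is none to reproduce. The check sets the sections side by side and then illustrates the scale.

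**1. What is needed.** The second clause of 18.1 and all of 18.3 need a recorded status before PrEP, including severity if worsening is to be judged.

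**2. What enrollment records.** The measures in 9.3, the baseline content in 10.1, the forms in 10.4 and the data sources in 12.2 include neither PRISE nor a symptom or medical-history form. Form AD2 in Appendix 10 asks for past medical history, but only for serious events and only after the event.

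**3. Which symptoms are asked about before PrEP.** Section 9.3 has all patients assessed for acute HIV symptoms, without listing them. The only itemized list is in the ICAP form (Appendix 5, section 6): fever, fatigue, sore throat, headache, and muscle pain or soreness, as part of one combined cold/flu question. Of these, only headache is a printed PRISE item, and a yes to the combined question does not show that headache was the reason.

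**4. What PRISE can pick up.** With a one-week recall, the day-30 form covers roughly days 30 − 7 = 23 to 30. Complaints that resolved before about day 23 are not captured. The concern is therefore confined to persistent or recurrent symptoms.

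**5. Illustration, on assumed rates.** The documents give no background symptom rate. Let b be the background prevalence of one PRISE symptom and n the number of PrEP takers completing the form. I take n = 40, the size of one arm in 11.1.3, and n = 20 as a lower case.

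With no drug effect, expected positive reports = n × b. If PrEP also causes the symptom in an assumed 10% of users, independently of background, the observed rate = 1 − (1 − b)(1 − 0.10).

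| b | n = 40, no drug effect | n = 20, no drug effect | Observed rate with 10% drug effect |
|---|---|---|---|
| 10% | 40 × 0.10 = 4 | 20 × 0.10 = 2 | 1 − 0.90 × 0.90 = 19% |
| 30% | 40 × 0.30 = 12 | 20 × 0.30 = 6 | 1 − 0.70 × 0.90 = 37% |
| 50% | 40 × 0.50 = 20 | 20 × 0.50 = 10 | 1 − 0.50 × 0.90 = 55% |

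These figures show only that background reports could be numerous compared with a modest drug effect. They are not estimates for this trial.

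**The case against.** The case on the other side is substantial, and it limits the point in several ways.

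- **A symptom review is called for.** A reader might infer that no symptom baseline is taken at all. The documents do not support that: 18.3 expressly covers current symptoms, acute HIV symptoms are assessed before PrEP, and consent covers extraction of clinical data from the medical record, where the presenting complaint should appear. The list in 9.3 is also not worded as exhaustive. What remains is that the review has no form or visit, and that an ED chart is not designed to cover PRISE items.
- **Change from baseline is not the whole AE definition.** It is the second of two clauses and depends on the investigator's judgement of clinical significance.
- **Attribution is a separate step.** A reader might infer that background symptoms are reported as PrEP side effects. No section says so. PRISE is neutral on cause, the investigator judges causality (18.5, 18.7), and form AD1 offers pre-existing disease as an alternative cause. This reduces the claim to a risk. It does not remove it, because that judgement is where a starting value is needed, and otherwise it rests on the chart or on recall by telephone at least 30 days later.
- **No PRISE rate is planned.** A reader might infer that the pilot will overstate PrEP intolerance in its planning data. Sections 11.1.2 and 21.0 contain no PRISE analysis or outcome, so the plan specifies no such estimate. This stands and lowers the severity.
- **A strict counting rule would err the other way.** Suppose a patient has withdrawal nausea at enrollment that resolves, and then drug-related nausea at day 30. Counting only new or worse symptoms would miss it unless it was rated worse. PRISE rates only the worst symptom in each domain, and the two levels printed are tolerable and distressing. This stands and shapes the fix.
- **Brevity is deliberate.** Section 10.1 defends a short ED assessment. That is a fair reason to add little, but one short form is little.

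**Conclusion.** The point holds as a gap in measurement. Sections 18.1 and 18.3 ask staff to separate pre-existing from new or worsening symptoms, but no enrollment form records a status matched to PRISE. PRISE starts at day 30 and, under 10.5.7, is given only to PrEP takers. Persistent or recurrent background symptoms risk misattribution, and worsening cannot be judged against an earlier rating.

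The size is unknown. The illustrative counts rest on assumed background rates, an assumed number of PrEP takers and, in the last column, an assumed independent 10% drug effect. The severity is minor to moderate: PRISE is not a listed outcome and causality is reviewed case by case, but the missing rating cannot be obtained later and is cheap to collect.

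**What to change.** Add PRISE to the enrollment assessments in 9.3 and 10.4 for all participants in both arms, completed before randomization and before any PrEP dose. State in 18.3 that it is to be used together with the history review when AEs are assessed.

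Report follow-up PRISE symptoms in two ways: as raw counts, and as new or worse than at enrollment. Do not exclude symptoms that were present at enrollment, because ED symptoms may be transient and the form rates only the worst symptom per domain.

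The cost is a few extra minutes on an ED assessment that 10.1 puts at 30 to 60 minutes, using a form the study already has. A baseline gives a within-person reference but no concurrent comparison with non-users, so the new-or-worse count should still not be read as a drug-effect rate.

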18.4 Adverse Event Reporting

Appropriately qualified and trained personnel will elicit participant reporting of AEs and SAEs (Appendix 10) at each follow-up assessment. Study personnel will obtain as much information as possible about the reported AE/SAE to complete the AE/SAE forms and will consult with the PI as necessary.

Standard reporting, within 7 days of the site becoming aware of the event, will be required for all AEs. Expedited reporting (within 24 hours of their occurrence and/or site's knowledge of the event) is required for reportable SAEs.

Reportable adverse events will be followed until resolution, stabilization or study end.

18.5 PIs Role in Assessing Severity and Causality of Adverse Events

The PI will conduct an initial assessment of the serious, severity and causality when eliciting participant reporting of adverse events.

18.6 Guidelines for Assessing Severity

The severity of an adverse event refers to the intensity of the event defined by CDISC SDTM Severity Intensity Scale for Adverse Event:

Grade 1	Mild	Transient or mild discomfort (typically <48 hours), no or minimal medical intervention/therapy required, hospitalization not necessary (non-prescription or single-use prescription therapy may be employed to relieve symptoms, e.g., aspirin for simple headache, acetaminophen for post-surgical pain)
Grade 2	Moderate	Mild to moderate limitation in activity, some assistance may be needed; no or minimal intervention/therapy required, hospitalization possible.
Grade 3	Severe	Marked limitation in activity, some assistance usually required; medical intervention/ therapy required, hospitalization possible.

18.7 Guidelines for Determining Causality

PI will use the following question when assessing causality of an adverse event to study medication where an affirmative answer designates the event as a suspected adverse reaction:

Is there a reasonable possibility that the study medication caused the event?

18.8 Site's Role in Monitoring Adverse Events

Staff education, re-training, or appropriate corrective action plan will be implemented as needed in response to reported AEs and SAEs.

18.9 Participant Withdrawal

The PI will apply his/her judgement to determine whether or not an adverse event is of sufficient severity to require that the participant be withdrawn from further study medication. A participant may also voluntarily withdraw from treatment due to what he/she perceives as an intolerable adverse event or for any other reason. If voluntary withdrawal is requested within the first 14-day and the patient was assigned to the iPrEP arm, the participant will be asked to complete an end-of-study medication visit to return unused medication and document end-of-medication outcomes.

19.0 Overall Structure of the Team

Research Team: The research team is comprised of experts in ED based public health program development and implementation. A project manager from the Mount Sinai Hospital Department of Emergency Medicine will provide administrative support. A TBN RA will undergo extensive training with the PI and the New York City Department of Health and Mental Hygiene (NYC DoHMH) to understand how to recruit, enroll and counsel the patients participating in this study. A TBN biostatistician will provide statistical support and analysis of the proposed studies.

Research Associate Training: RAs will undergo two weeks of training that includes both didactic course work and shadowing. The didactic course work is offered by the New York City Department of Health and Mental Hygiene through the Training and Technical Assistance Program. Required courses for the RAs will include Understanding HIV infection, diagnosis and treatment (1-day), PEP, PrEP and Other Biomedical Interventions (1-day), Best Practices in PrEP/PEP Education & Counseling (1-day), Fundamentals of HIV Prevention Counseling (2-days) and Motivational Interviewing (2-day) and Improving linkage to care using the “ARTAS” model (2-days).⁷⁶ Didactic training will occur in the first two months of the grant. RAs will shadow [name] for 1 week prior to the start of the RCT to familiarize themselves with linkage pathways and mechanisms, PrEP counseling, adherence counseling and risk reduction counseling

20.0 Interventions

Intervention Type	Randomized Controlled Clinical Trial
Name	Pre-Exposure Prophylaxis Provision in the Emergency Department (PrEPPEDE Trial)
Description	Compare the impact of immediate PrEP initiation in the Emergency Department by providing a PrEP “starter pack” with facilitated linkage to care versus facilitated linkage to care for out-patient PrEP initiation within 14 days of the Emergency Department visit.

21.0 Outcome measures

Secondary Outcome 1:	Retention in PrEP care at 30, 60, and 90 days post PrEP index visit
Type	Secondary
Time frame	30, 60 and 90 days
Description	# of patients retained in care at 30, 60 and 60-days post-PrEP initiation

Secondary Outcome 2: PrEP usage post PrEP index visit

Type	Secondary
Time frame	30, 60 and 90 days
Brief description	# of patients still using PrEP at 30 and 60-days post PrEP initiation

Secondary Outcome 3:	PrEP adherence at follow up post PrEP index visit
Type	Secondary
Time frame	30, 60, 90 days
Brief description	Level of adherence to PrEP at 30, 60, 90-days post PrEP initiation

Secondary Outcome 4:	Risk behavior post PrEP index visit
Type	Secondary
Time frame	30, 60, 90 days
Brief description	HIV risk behaviors at 30, 60, 90-days post PrEP initiation

Secondary Outcome 5:	STI diagnoses post PrEP index visit
Type	Secondary
Time frame	30, 60, 90 days
Brief description	# and type of STI diagnosed at 30 and 90-day post PrEP initiation visits

Secondary Outcome 6:	HIV infection
Type	Secondary
Time frame	90-days
Brief description	# of new HIV infections, if any, at 90-days post PrEP initiation

Secondary Outcome 7:	Program Satisfaction
Type	Secondary
Time frame	90-days
Brief description	Program satisfaction at 30, 60 and 90-day follow-up

22.0 FDA Regulated Intervention

For this intervention, we do not require an Investigational New Drug application to the FDA.

Emtricitabine/tenofovir disoproxil fumarate and emtricitabine and tenofovir alafenamide are both FDA approved for Pre-Exposure Prophylaxis for HIV and meet all of the requirements for an IND exemption as described in 21 CFR 312.2(b). These include:

- 1) The drug product is lawfully marketed in the United States.
- 2) The investigation is not intended to be reported to FDA as a well-controlled study in support of a new indication and there is no intent to use it to support any other significant change in the labeling of the drug.
- 3) In the case of a prescription drug, the investigation is not intended to support a significant change in the advertising for the drug.
- 4) The investigation does not involve a route of administration, dose, patient population, or other factor that significantly increases the risk (or decreases the acceptability of the risk) associated with the use of the drug product (21 CFR 312.2(b) (1) (iii)).
- 5) The investigation is conducted in compliance with the requirements for review by an IRB (21 CFR part 56) and with the requirements for informed consent (21 CFR part 50).
- 6) The investigation is conducted in compliance with the requirements of § 312.7 (i.e., the investigation is not intended to promote or commercialize the drug product).

Effective Date: 4/20/2021

End Date: 3/18/2022

23.0 Dissemination Plan

23.1 Clinicaltrials.gov Requirements

This project includes applicable clinical trials which require registration in ClinicalTrials.gov. In accordance with Public Law 110-85 the trials will be registered with clinicaltrials.gov prior to the enrollment of the first participant. Reporting of summary results will occur no later than 1 year after the completion date of the last enrolled participant. All grant and progress report forms shall include a certification that the responsible party has made all required submissions to ClinicalTrials.gov. The responsible party for all clinicaltrials.gov reporting will be the PI, [name].

23.2 Informed consent

A description of this clinical trial will be available on the website, <http://www.ClinicalTrials.gov>, as required by U.S. Law. The National Institutes of Health (NIH) encourages all researchers to post their research. This Web site will not include information that can identify you. At most, the Web site will include a summary of the results. You can search the Web site at any time.

APPENDIX

Appendix 1: Locator Form

Name: _____

First MI Last

Nick Name (s): _____

2. Age: _____ Date of Birth: _____ / _____ / _____

3. MRN: _____

4. Where do you currently live?

Address _____ Apt No.: _____

City _____ State _____ Zip Code: _____

Type of dwelling: _____

Whose place is it? _____

Name Relationship

5. Is this the best address where we can send you information?

Address _____ Apt No.: _____

City _____ State _____ Zip Code: _____

6. What is the best way we should contact you by?

Regular mail Email Phone Text

7. Primary phone number: (_____) _____ Cell Work Home

Share phone? No Yes With whom? _____

If we leave a message for you, what can we say? OK to text? Yes No

Mount Sinai BI Hospital Navigator

Other: _____

8. OK to text primary number? Yes No

9. Alternative phone number: (_____) _____ Cell Work Home

If we leave a message for you, what can we say?

Mount Sinai BI Hospital Navigator

Other: _____

10. OK to text alternative number? Yes No

Email address: _____

12. Which of the above is the best way to reach you quickly, if necessary?

Specify: _____

13. May we contact you at work? Yes No Not working

Name of employer: _____

Work Address: _____

City: _____ State: _____ Zip: _____

Phone: _____

Can we leave a message at this number? Yes No

If yes, what can we say?

Mount Sinai BI Hospital Navigator

Other: _____

14. OK to text work number? Yes No

SECONDARY CONTACT INFORMATION: Parent, sister/brother, other relative, good friend, neighbor, case worker/social worker or counselor. If not in contact with the person within the last month, ask for another contact.

CONTACT #1

14. Name: _____

Address: _____

Phone: (____) _____

What is your relationship to this person? _____

If we leave a message with them for you, what can we say?

Mount Sinai BI Hospital Navigator

Other: _____

CONTACT #2

15. Name: _____

Address: _____

Phone: (____) _____

What is your relationship to this person? _____

If we leave a message with them for you, what can we say?

Mount Sinai BI Hospital Navigator

Other: _____

Appendix 2: Satisfaction Measure

Exposure Prophylaxis Provision in the Emergency Department (PrEPPED)
action and Acceptability Measures

all satisfaction with the screening procedures

How inconvenient did you find today's screening procedures?

Not Inconvenient 0	1	2	3	4	5	Very Inconvenient 6	Prefer not to answer
-----------------------	---	---	---	---	---	------------------------	----------------------

How difficult did you find today's screening procedures?

Not at all difficult 0	1	2	3	4	5	Very Difficult 6	Prefer not to answer
---------------------------	---	---	---	---	---	---------------------	----------------------

How satisfied were you with today's screening process?

Very dissatisfied 0	1	2	3	4	5	Very satisfied 6	Prefer not to answer
------------------------	---	---	---	---	---	---------------------	----------------------

